### 8.1.1.1 PROCEDURES BY STUDY VISIT

#### Screening Visit (Visit 1, Days -7 to -21)

The goal of this visit is to explain the study to potential participants, obtain informed consent/assent, and collect a brief medical history and laboratory studies to assess inclusion/exclusion criteria. After the Screening Visit is complete, eligible participants will begin the run-in period.

1. Inclusion/exclusion criteria will be reviewed. This will include age, BMI, asthma diagnosis, and ability to swallow pills, confounding medical conditions, and concomitant medications per protocol.
2. Informed consent/assent will be obtained for eligible participants (see Section 10.1.1). Once consent and assent have been obtained, the participant is enrolled in the study.
3. Demographic data will be recorded on the data collection form along with measured height and weight.
4. Medical history, including history of asthma exacerbations, will be obtained.
5. Participants (parent/guardian and child) will be asked to initial a form documenting whether they prefer to have this visit 1 blood sample taken from the child's arm or taken from a fingerstick.
6. Participants meeting all other eligibility criteria will have samples collected for local serum 25(OH) vitamin D assessment, urine pregnancy test (for female participants of child-bearing potential), and urine calcium/creatinine ratio.
7. Local safety measures (as described in Section 8.2) will be reviewed by the study coordinator to determine eligibility for continued enrollment. If any safety laboratory value exceeds the thresholds defined by protocol, the participant will be referred to the participant's primary care physician.
8. Diary cards, (without the line to record Vitamin D dosing), will be given to the participant and instructions for completion of the diary will be reviewed. These diary cards will have the questions about asthma control and symptoms and asthma medications, but will not have the questions about vitamin D dosing.

## **Baseline (Visit 2, Day 0)**

Study Visit 2 must occur between 10 and 21 days, with a target of 14 days, after Study Visit 1. The goal of this visit is to review eligibility for continued enrollment, provide study procedure training, and randomize participants.

1. Interval history (concomitant medications, asthma symptoms, healthcare utilization) and diary cards (without the line to record Vitamin D dosing) will be reviewed at Visit 2 to assess eligibility for study participation.
  - a. Site must confirm that participant continues to meet inclusion/exclusion criteria except for age less than 18 years.
  - b. To be randomized, participants must complete and return diary cards with a completion rate greater than or equal to 75%. Participants who do not meet this level of adherence will be removed from the study.
2. An ACT or c-ACT will be completed by the caregiver and/or child, as appropriate.
3. Height and weight measurements for calculation of BMI and BMI-percentile.
4. Blood draw (by venipuncture) for central laboratory 25(OH)D level determination and inflammatory marker assays.
5. Study drug will be dispensed and dosing explained to the participant and his or her parent, legal guardian, or caregiver. (See Section 6.1.2).
6. Diary cards for dosing visits will be given to the participant and instructions for completion of the diary will be reviewed.
7. Study Visit 3 will be scheduled for 28 days ( $\pm 7$ ) from Study Visit 2.

## **Weeks 1-3 (no mandatory visits; optional visit for PK blood draw)**

Adherence communications will occur at least biweekly (every 2 weeks) between study Visits 2 and 3. The study coordinator will interact with the participants and his or her parent, legal guardian, or caregiver through text message, phone, or email to encourage continued participation in the study, monitor adherence to medications, and ask about interval asthma symptoms.

Sites will ask participants to return for serum 25(OH)D level between 1-3 weeks (days 7 to 21, inclusive) after the first dose of vitamin D. Every effort will be made to collect this sample, but this blood draw will be optional. If the participant consents to the optional visit, the participant (parent/guardian and child) will be asked to initial a form documenting whether they prefer to have this visit's blood sample taken by venipuncture or fingerstick.

### **Study Visit 3 (Week 4, Day 28 [ $\pm 7$ ])**

1. Unused medication will be returned and the study coordinator will review the diary cards for dosing visits.
2. ACT (or c-ACT) will be completed by the caregiver and/or child as appropriate.
3. Interval history will be reviewed and recorded including asthma exacerbations, unplanned healthcare utilization, new or changes in concomitant medications (including asthma medications) and adverse events.
4. Height and weight measurements for calculation of BMI and BMI-percentile.
5. Urine will be obtained for calcium/creatinine ratio.
6. Participants (parent/guardian and child) will be asked to initial a form documenting whether they prefer to have this visit's blood sample taken by venipuncture or fingerstick.
7. Blood for 25(OH)D level (required) and inflammatory markers (if blood drawn by venipuncture) will be obtained and sent to central laboratory.
8. Study drug will be dispensed and dosing reviewed with the participant and his or her parent, legal guardian, or caregiver. (See Section 6.1.2)
9. Diary cards for dosing visits will be given to the participant and instructions for completion of the diary will be reviewed.
10. Study Visit 4 will be scheduled for 56 days ( $\pm 7$ ) from Study Visit 2 (baseline).
11. If a participant is withdrawn from the study drug, he/she will be asked to continue to make any remaining study visits in order to assure his/her safety. (See Section 7.1)

### **Weeks 5-7 (No Scheduled Visits)**

Adherence communications will occur at least biweekly (every 2 weeks) between study Visits 3 and 4. The study coordinator will interact with the participants and his or her parent, legal guardian, or caregiver through text message, phone, or email to encourage continued participation in the study, monitor adherence to medications, and ask about interval asthma symptoms.

### **Study Visit 4 (Week 8, Day 56 [ $\pm 7$ ])**

1. Unused medication will be returned and the study coordinator will review the diary cards for dosing visits.
2. ACT (or c-ACT) will be completed by the caregiver and/or child as appropriate.
3. Interval history will be reviewed and recorded including asthma exacerbations and adverse events.
4. Concomitant medications will be reviewed and recorded.
5. Height and weight measurements for calculation of BMI and BMI-percentile.
6. Urine will be obtained for calcium/creatinine ratio (all participants) and for pregnancy tests (for female participants of child-bearing potential).
7. Participants (parent/guardian and child) will be asked to initial a form documenting whether they prefer to have this visit's blood sample taken by venipuncture or fingerstick.
8. Blood for 25(OH)D level (required) and inflammatory markers (if blood drawn by venipuncture) will be obtained and sent to central laboratory.
9. Study drug will be dispensed and dosing reviewed with the participant and his or her parent, legal guardian, or caregiver. (See Section 6.1.2)
10. Diary cards for dosing visits will be given to the participant and instructions for completion of the diary will be reviewed.
11. Study Visit 5 will be scheduled for 84 days ( $\pm 7$ ) from Study Visit 2 (baseline).

### **Weeks 9-11 (No Scheduled Visits)**

Adherence communications will occur at least biweekly (every 2 weeks) between study Visits 4 and 5. The study coordinator will interact with the participants and his or her parent, legal guardian, or caregiver through text message, phone, or email to encourage continued participation in the study, monitor adherence to medications, and ask about interval asthma symptoms.

### **Study Visit 5 (Week 12, Day 84 [ $\pm 7$ ])**

1. Unused medication will be returned and the study coordinator will review the diary cards for dosing visits.
2. ACT (or c-ACT) will be completed by the caregiver and/or child as appropriate.
3. Interval history will be reviewed and recorded including asthma exacerbations and adverse events.
4. Concomitant medications will be reviewed and recorded.
5. Height and weight measurements for calculation of BMI and BMI-percentile.
6. Urine will be obtained for calcium/creatinine ratio.
7. Participants (parent/guardian and child) will be asked to initial a form documenting whether they prefer to have this visit's blood sample taken by venipuncture or fingerstick.
8. Blood for 25(OH)D level (required) and inflammatory markers (if blood drawn by venipuncture) will be obtained and sent to central laboratory.
9. Study drug will be dispensed and dosing reviewed with the participant and his or her parent, legal guardian, or caregiver. (See Section 6.1.2).
10. Diary cards for dosing visits will be given to the participant and instructions for completion of the diary will be reviewed.
11. Study Visit 6 will be scheduled for 112 days ( $\pm 7$ ) from Study Visit 2 (baseline).

### **Weeks 13-15 (No Scheduled Visits)**

Adherence communications will occur at least biweekly (every 2 weeks) between study Visits 5 and 6. The study coordinator will interact with the participants and his or her parent, legal guardian, or caregiver through text message, phone, or email to encourage continued participation in the study, monitor adherence to medications, and ask about interval asthma symptoms.

### **Study Visit 6 (Week 16, Day 112 [ $\pm 7$ ])**

1. Unused medication will be returned and the study coordinator will review the diary cards for dosing visits.
2. ACT (or c-ACT) will be completed by the caregiver and/or child as appropriate.
3. Interval history will be reviewed and recorded including asthma exacerbations and adverse events.
4. Concomitant medications will be reviewed and recorded.
5. Height and weight measurements for calculation of BMI and BMI-percentile.
6. Blood for 25(OH)D level and inflammatory marker assays will be drawn by venipuncture and sent to central laboratory.
7. Urine will be obtained for calcium/creatinine ratio (all participants) and for pregnancy tests (for female participants of child-bearing potential).
8. Diary cards without the line to record Vitamin D dosing will be given to the participant/parent/guardian. These diary cards have the questions about asthma control and symptoms and asthma medications, but do not have the questions about vitamin D dosing. These will be the same cards as those given at Visit 1 (screening visit).
9. Follow-up visit for week 20 (visit 7) will be scheduled for 140 days ( $\pm 7$  days) from Study Visit 2 (baseline).

### **Follow-up Visits: Weeks 20 (visit 7), 24 (visit 8), and 28 (visit 9) [Days 140, 168, and 196, respectively, each $\pm 7$ days]**

1. Participants (parent/guardian and child) will be asked to initial a form documenting whether they prefer to have this visit's blood sample taken by venipuncture or fingerstick.
2. Post-dosing blood draw for 25(OH)D level (required) and inflammatory markers (if blood drawn by venipuncture) will be obtained and sent to central laboratory.
3. At weeks 20 (visit 7; day 140  $\pm 7$ ) and 24 (visit 8; day 168  $\pm 7$ ) only, diary cards without the line to record vitamin D dosing will be given to the participant/parents/guardian. Instructions for completion of the diary will be reviewed. These diary cards will have questions about asthma control and symptoms and asthma medications but will not have any questions about vitamin D. These will be the same cards as those given at Visit 1 (screening visit).

4. Diary cards from the previous visit, as well as additional interval history, will be reviewed. Information, including asthma exacerbations and adverse events, will be recorded.
5. Follow-up visit for week 24 (visit 8) will be scheduled for 168 ( $\pm 7$ ) days from Visit 2 (baseline) and follow-up visit for week 28 (visit 9) will be scheduled for 196 ( $\pm 7$ ) days from Visit 2 (baseline).
6. At week 28 (visit 9; day 196  $\pm 7$ ), local serum 25(OH)D level will be determined. This is in addition to the central lab.
7. Coordinators will call, text, or email participants at least the week prior to their visit as a reminder.

#### 8.1.1.2 ASTHMA MEASURES

##### **Asthma Control Test (ACT)**

The ACT is a 4-week recall questionnaire that has been validated and addresses issues of asthma control, symptoms, and nocturnal awakenings for patients with asthma aged 12 and above.(82) The ACT will be administered to 12 to 18-year-olds at all in-person clinic visits.

##### **Childhood Asthma Control Test (c-ACT)**

The c-ACT is a 4-week recall questionnaire that has been validated and addresses issues of asthma control, symptoms, activity limitation, and nocturnal awakenings for patients aged 4 to 11 years with asthma). The c-ACT will be administered to 6 to 11- year-olds at all in-person visits.

Participants that turn 12 during the course of the study will continue to use the c-ACT test for the duration of their participation.

##### **Asthma-related Events**

The presence of asthma-related events (ASDs, exacerbations, episodes of problematic asthma, respiratory infections) will be identified by participant documentation on daily diary cards (collected at all clinic visits) and by structured interviews at in-person clinic visits.

###### **1. ASDs:**

A diary card will be used to compile information about asthma symptoms. Though diary cards similar to those proposed for VDORA have been used successfully in large highly-controlled pediatric asthma trials, symptom diaries can be criticized for some participants having incomplete data. Symptom diaries however can be used successfully particularly in intervention trials less than 26 weeks (as with VDORA) and when participants are frequently reminded and supported closely by research staff. (76, 77)

An ASD (83) will be defined as a day with any one of the following:

- a. Albuterol rescue use (pre-exercise treatment permitted)
- b. Use of additional asthma medications including oral steroids. In addition, the 7 days immediately following the end of a course of oral steroids will be considered ASDs.
- c. Daytime or nighttime asthma symptoms (wheezing, coughing, phlegm/mucus, chest tightness, or shortness of breath)
- d. Unscheduled health care provider visits for asthma, emergency room visit or hospital admission for asthma, or missed work or school due to asthma

Baseline frequency of ASDs will be documented for each participant using the participant's run-in period and Week 1 (if needed) diary cards to explore changes in mean ASD/week longitudinally on treatment.

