### 5.2 EXCLUSION CRITERIA

An individual who meets any of the following exclusion criteria will be excluded from participation in the study:

- Known diseases of calcium metabolism or the parathyroid
- History of renal insufficiency or kidney stones
- Known liver failure or history of abnormal liver function which is deemed by the site investigator to be clinically significant
- History of Williams syndrome, sarcoidosis, or granulomatous disease
- Active tuberculosis

- Spot urine calcium/creatinine ratio greater than 0.37 on 2 consecutive visits. If the ratio is greater than 0.37 on the first visit, this test must be repeated once - following adequate hydration, within 2 business days of the study team being notified of the initial lab results.
- Clinical evidence of rickets
- Taking supplemental vitamin D greater than 1000 IU per day
- Administration of an excluded medication (systemic glucocorticoids, drugs affecting calcium metabolism, drug affecting fat absorption) within 30 days prior to study enrollment – at screening (Visit 1) or at any time during the run-in period.
- Other medical issues that in the opinion of the investigator put the participant at risk or affect results of the study (e.g., fat malabsorption, cystic fibrosis, chronic lung disease of prematurity, congenital heart disease). Type 2 diabetes is not an exclusion criterion.
- Plans to move out of the study area in the next 9 months
- There is another child in the household enrolled in the study
- Plans for significant lifestyle changes in the next 9 months (significant dietary changes while enrolled in the study)
- Participants who are eligible for the run-in period will be ineligible for randomization if they do not demonstrate adherence to run-in procedures (return diary cards with a completion rate greater than or equal to 75%)

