### 6.1.2 DOSING AND ADMINISTRATION

Once the assigned dose of vitamin D3 is determined, it will be dispensed by the site to the participant's caregiver at Visit 2 (baseline). The caregiver will be instructed to give the participant a loading dose of one 50,000 IU capsule orally on the day of the baseline

visit if the child is randomized to a loading dose cohort. Thereafter, participants will take their assigned vitamin D3 dose (600, 6000, or 10,000 IU (part 1) or 600 or 8,000 IU (part 2)) orally each day, starting on the day after the baseline visit and continuing to Visit 6. Participants with no loading dose will start on their daily dose on the day of the baseline visit. A member of the study team will witness and document the initial dose for each participant during the baseline visit. Participants will be given a dosing diary for recording all doses of vitamin D3 taken through the 16-week dosing phase. Missed doses will also be noted in the daily diary cards for dosing visits.

Following the interim analysis, an optimal dosing regimen was recommended for Part 2.

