### 6.2.2 FORMULATION, APPEARANCE, PACKAGING, AND LABELING

All vitamin D3 doses will be packed in blister packs or individually labeled bottles. The loading doses will be packaged separately from the daily doses; loading doses will be given directly to participants to take during visit 2. Participants will take home the labeled bottles/packs for their daily (i.e., all but visit 2) doses. Vitamin D supplements will be provided in the form of a size 2 capsule, either gelatin or hypromellose (vegetable). The capsules used for all doses in Part 1 were gelatin. The D3 (4000 IU) capsules for Part 2 are vegetable capsules. Size 2 capsules are approximately 18 mm in length (0.71 inches) with an outside diameter of 6.3 mm (0.24 inches).

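### The baseline for the exploratory asthma-symptom-day change may include open-label Week 1 diaries recorded after the first dose, with no rule for when

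*Combined protocol and SAP*

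**What the plan says.** Section 8.1.1.2, item 1 (ASDs), documents each child's baseline ASD frequency "using the participant's run-in period and Week 1 (if needed) diary cards" and gives its purpose: "to explore changes in mean ASD/week longitudinally on treatment". It does not say what makes Week 1 needed, how many run-in days are enough, or who decides.

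Other sections place Week 1 after the first dose:

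- Section 6.1.2, all cohorts: "A member of the study team will witness and document the initial dose for each participant during the baseline visit". For cohorts without a load: "Participants with no loading dose will start on their daily dose on the day of the baseline visit".
- Section 6.2.2: "loading doses will be given directly to participants to take during visit 2".
- Section 8.1.1.1, Weeks 1-3, counts weeks from dosing: the optional blood draw falls "between 1-3 weeks (days 7 to 21, inclusive) after the first dose of vitamin D".
- Section 8.1.1.1, Baseline (Visit 2): "Diary cards for dosing visits will be given to the participant and instructions for completion of the diary will be reviewed". Week 1 is therefore recorded on the dosing-phase card.
- Section 6.3: the study is not masked.

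Before randomization, Section 5.2 requires participants to "return diary cards with a completion rate greater than or equal to 75" percent. Section 9.4.10 plans estimating-equation models for ASDs over time and does not restate the baseline window.

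**The concern.** A reference value for change on treatment should come from before treatment. Here one set of days is treated as baseline by the ASD definition and as dosing time by the dosing, packaging and visit sections. Two things then enter the reference value: any early effect of the dose, and any change in reporting once the family knows the arm. They enter only for the children in whom Week 1 is used, and the plan leaves that choice undefined. Nothing removes Week 1 from the on-treatment series either, so the same days could be counted on both sides of the comparison.

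The two windows also differ in a way that does not depend on vitamin D. Section 5.2 excludes systemic glucocorticoids during the run-in (Section 6.5 sets the threshold at more than 10 mg/day), while Sections 6.5 and 6.5.1 allow them for acute asthma after dosing starts. The ASD definition counts oral-steroid days, and the 7 days after a course, as symptom days. A steroid course in Week 1 could therefore raise the baseline by a route largely closed during the run-in.

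What is at stake is the ASD/week change, which the study explores with a future intervention trial in view.

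**Working it through.** The plan states no figure for the size of this effect, so there is none to reproduce. The check has three steps.

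**1. Share of the baseline that is post-dose.** Inputs:

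- Run-in length: target 14 days. The minimum is 10 days in the Visit 2 text of Section 8.1.1.1, but 7 days in Table 1 footnote a and the Visit 1 heading. The maximum is 21 days in all three.
- Completion: 100%, or the 75% minimum, taken here as a share of days.
- Week 1: all 7 days completed.

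Formula: w = 7 / (7 + completed run-in days).

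| Run-in | Completed days at 100% | w | Completed days at 75% | w |
|---|---|---|---|---|
| 21 days | 21 | 7/28 = 25% | 15.75 | 7/22.75 = 31% |
| 14 days | 14 | 7/21 = 33% | 10.5 | 7/17.5 = 40% |
| 10 days | 10 | 7/17 = 41% | 7.5 | 7/14.5 = 48% |
| 7 days | 7 | 7/14 = 50% | 5.25 | 7/12.25 = 57% |

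The last row applies only if a 7-day run-in is allowed, which the Visit 2 text does not permit.

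**2. Effect on the measured change.** Let R be the run-in ASD/week, R + d the Week 1 rate, and T the later on-treatment rate. Pooling days gives a baseline of (1 − w)R + w(R + d) = R + wd. The measured change is T − R − wd, so it is off by wd. If d has the same sign as T − R, the change shrinks. If d has the opposite sign, the change is inflated.

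Write d = f(T − R), where f is the fraction of the later effect already present in Week 1. The proportional loss is then wf. For w = 0.33 to 0.40:

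- f = 0.1: 3% to 4%
- f = 0.5: 17% to 20%
- f = 1: 33% to 40%

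**3. A plausible f if effect follows drug accumulation (an assumption).** The documents give no onset time for ASDs. Section 8.2 gives a half-life of about 2 months and Section 2.2 gives 2 to 3 months, so h = 60 or 90 days. Use a one-compartment sum with no absorption delay: A(t) = L·e^(−kt) + Σ D·e^(−k(t−s)), with k = ln 2 / h, L the load, D the daily dose, and daily doses starting on day 1 after a load or day 0 without one. Then f is mean A over days 0–6 divided by mean A over days 105–111.

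| Cohort | f, h = 60 | f, h = 90 |
|---|---|---|
| Part 2 Cohort A (50,000 + 8,000) | 0.141 | 0.119 |
| Part 1 Cohort 1 (50,000 + 6,000) | 0.171 | 0.144 |
| Part 1 Cohort 2 (50,000 + 10,000) | 0.122 | 0.104 |
| No load (6,000 or 600) | 0.063 | 0.053 |

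The loss wf for w = 0.333 to 0.40 is:

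- Loading cohorts overall: 0.333 × 0.104 = 3.5% to 0.40 × 0.171 = 6.8%.
- Cohort A: 0.333 × 0.119 = 4.0% to 0.40 × 0.141 = 5.6%.
- No-load cohorts: 0.333 × 0.053 = 1.8% to 0.40 × 0.063 = 2.5%.

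On this assumption the loss is small, arises only in children whose Week 1 is used, and differs by arm. It does not cover an open-label reporting shift or a steroid course, which need not follow accumulation.

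**The case against.** The case for leaving the text alone has weight.

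- ASD is one of five exploratory endpoints, the baseline is said to be for exploration, and Section 8.2 states that this is not a trial of asthma treatment. Section 9.4.10 names no between-arm ASD test. All of this stands and limits the weight of the point.
- The 75% diary rule means Week 1 should seldom be needed. This stands too. It also means that dropping Week 1 should cost little.
- Vitamin D accumulates slowly, so an early drug effect should be small. That is fair if effect follows exposure. It does not address reporting with the arm known, or the different steroid rules in the two windows.
- If the proviso means too few run-in days, the need is settled at Visit 2 before assignment and is unrelated to arm. That is the natural reading, but the plan does not state it. Even then, the Week 1 days themselves are recorded after assignment.
- Section 9.4.1 defers detail to a separate SAP. No separate SAP text is in the document reviewed, so whether it settles the window could not be checked.

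**Conclusion.** The concern holds at exploratory weight. As written, the rule lets post-dose, open-label diary days into the reference for on-treatment change, with no trigger. In an affected child, Week 1 would be 33% of baseline days for a full 14-day run-in, 40% at 75% completion, and 41% for a full 10-day run-in. The measured change moves by that share of any Week 1 shift. These shares assume a full Week 1 pooled by day with the run-in. The number of affected children is unknown but probably small.

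A reader might infer three stronger things that the documents do not support:

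- **That the change is biased toward zero.** This is true only if the Week 1 shift has the same sign as the later change, and the documents give neither sign nor size.
- **That a third to a half of the effect is lost.** The shares describe diary days. They equal the loss only if the full later effect is already present in Week 1. The 50% share also needs a 7-day run-in, on which the protocol disagrees with itself.
- **That the trial's main conclusions are at risk.** The PK analysis, the Part 2 25(OH)D responder test, the sample size and the safety analyses do not use this baseline.

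**What to change.** In Section 8.1.1.2, and in the SAP to match:

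1. Define baseline ASD/week from run-in diary days before the first dose only: 7 × symptom days / completed days.
2. State a minimum number of completed days, and treat baseline as missing below it. Deleting the reference to Week 1 is not enough without this rule, since 75% completion leaves 7.5 days from a 10-day run-in and 5.25 from a 7-day one.
3. Count Week 1 only as on-treatment data, or use it as baseline only in a labelled sensitivity analysis.
4. Reconcile the minimum run-in length between Table 1 footnote a and the Visit 1 heading (7 days) and the Visit 2 text (10 days), because it sets how many pre-dose days exist.

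The cost is a few lines of text. No visit, sample, sample size or power figure changes. The downside is a slightly noisier, or occasionally missing, baseline for a few children with short run-ins.
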